11.9.4 Vital Signs

Absolute values and changes for vital signs from pre-dose to Day 5 or discharge will be documented. The maximum deviation of BP from Baseline between drug and placebo control groups (systolic and diastolic) to 24 Hours will be analyzed using ANCOVA, including factors for treatment group.

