1.7 Definitions

Baseline: A subject's baseline value for a given endpoint or parameter is defined as his/her latest measurement taken prior to study drug administration.

Prior and Concomitant Medications: Prior medications are defined as those taken within three days of treatment initiation. Concomitant medications are defined as those taken during study drug administration or after study drug has been administered through and including the Day 30 visit. All prior and all concomitant medications will be recorded on the electronic case report form (e-CRF).

Randomization: The time of randomization is defined as the time randomization occurred on the central server and this time is considered time zero for the study. All time windows are calculated from the time of randomization.

Treatment-Emergent Adverse Event: A treatment-emergent adverse event (TEAE) is one that first occurs or worsens in severity or frequency after study drug has been administered through to and including the Day 30 visit. SAEs are collected through the last study visit. Those AEs that start at the same time and date as the study drug administration and those that first occur or worsen after the start of study drug administration will be considered TEAEs.

AEs with partial or missing dates will be handled as follows:

- If the start day and/or month of the AE is missing and the AE in question occurs concurrently or subsequent to the study drug administration, the AE will be considered treatment-emergent.
- If the start date is completely missing then the AE will be considered treatment-emergent.

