6.0 STATISTICAL METHODS

The software used for all summary statistical analyses will be SAS® (SAS Institute, Inc.) version 9.4 or later.

Unless otherwise noted, categorical data will be summarized for each treatment group using counts and percentages, with the denominator for percentages being the number of subjects in the population of interest. Unless otherwise noted, continuous data will be summarized for each treatment group using the number of observations (n), mean, standard deviation (SD), median, minimum, and maximum. Some continuous data will be reported as the median, interquartile range (IQR), minimum and maximum according to the clinical meaning of the data.

Percentages will be rounded to one decimal place, except 0% and 100% will be displayed without any decimal places. Minima and maxima will be rounded to the precision of the original value; means and medians will be rounded to one decimal place greater than the precision of the original value; SDs will be rounded to two decimal places greater than the precision of the original value. P-values will be reported to four decimal places (0.xxxx), with values less than 0.0001 presented as <0.0001.

Inferential analyses will generally include statistics such as 2-sided 95% confidence intervals (CI), and p-values. Unless stated otherwise, all statistical tests will be 2-sided hypothesis tests performed at the 0.05 level of significance.

In order to protect the overall trial false positive rate, the primary efficacy analysis, key secondary outcome analysis and secondary endpoints will be analyzed in a fixed sequence, stopping and calling all subsequent analyses exploratory (and accepting the null hypothesis) at the first failed hypothesis test in the sequence. The fixed sequential order is:

1. Primary efficacy outcome
2. Key secondary outcome analysis (shift analysis using proportional odds model);
3. Secondary efficacy endpoints, as specified in the order presented below in Section 6.7.

All data will be included in subject data listings for all randomized subjects.

A final, unblinded, statistical report that will include both efficacy and safety evaluations will be generated upon completion of the trial. The final report will be distributed to the Trial Steering Committee

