8.2 Vital Signs

Vital signs will be taken in the supine position at Baseline (pre-dose), at the completion of drug infusion, and at 24 Hours, 48 Hours and Day 5/discharge. Vital signs including temperature, systolic and diastolic blood pressure, heart rate, and weight will be

reported by assessment time. Absolute values and changes for vital signs from pre-dose to Day 5 or discharge will be documented. The maximum deviation of BP from Baseline between drug and placebo control groups (systolic and diastolic) to 24 Hours will each be analyzed using ANCOVA, including factors for treatment group, the use of general anesthesia and treatment with intravenous alteplase, three factors that may affect blood pressure. Results will be tabulated and listed by treatment group and timepoint.

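### The only inferential blood-pressure safety analysis leaves out baseline blood pressure, and so may be less precise than it could be at no cost; the gain depends on how maximum deviation is defined

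*SAP*

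**What the plan says.** SAP 8.2 states the outcome and method: "The maximum deviation of BP from Baseline between drug and placebo control groups (systolic and diastolic) to 24 Hours will each be analyzed using ANCOVA". The model terms follow: "including factors for treatment group, the use of general anesthesia and treatment with intravenous alteplase". The same sentence goes on to count these as three factors. Protocol 11.9.4 gives a shorter version, in which the deviation "will be analyzed using ANCOVA, including factors for treatment group". No other section of either document adds baseline BP to this model.

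The baseline value is available. SAP 8.2 schedules it: "Vital signs will be taken in the supine position at Baseline (pre-dose), at the completion of drug infusion", with further readings at 24 hours, 48 hours and Day 5 or discharge. SAP 1.7 defines baseline as the "latest measurement taken prior to study drug administration".

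Neither document says whether maximum deviation is signed, absolute or the largest fall.

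**The concern.** Subtracting baseline is not the same as adjusting for it. Subjects whose pre-dose pressure happens to be high tend to fall, and those with a low value tend to rise, so the deviation usually stays correlated with baseline. A model without baseline leaves that predictable variation in the error term. It also lets a chance difference in baseline BP between arms pass into the treatment estimate. BP is not among the stratification or minimization variables (Protocol 6.2), so the randomization does not steer towards balance on it.

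BP lowering is a potential risk in these documents. Protocol 10.2.3 reports transient hypotension in animals at doses above the trial dose. Protocol 4.4.1 gives decreased BP in 11% of Phase 1 subjects on NA-1. Protocol 4.4.2 gives hypotension in 6% of placebo and 10% of NA-1 subjects in Phase 2. SAP 8.2 contains the only inferential BP comparison, and in a safety analysis avoidable imprecision makes a real effect easier to miss.

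**Working it through.** **Inputs.** From the documents: the outcome and model terms (SAP 8.2, Protocol 11.9.4); a pre-dose reading, with end-of-infusion and 24-hour readings inside the window (SAP 8.2); and the rule that "all statistical tests will be 2-sided hypothesis tests performed at the 0.05 level of significance" (SAP 6.0). The documents state no SD, correlation or power for this analysis, so there is no plan figure to reproduce. I assume a baseline-to-post-dose correlation ρ and equal SDs s. The comparison also takes baseline BP as unrelated to the other model factors.

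**Step 1: a single change score.** Let X be baseline and Y one post-dose reading.

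- Without baseline: Var(Y − X) = 2s²(1 − ρ).
- With baseline: residual variance = s²(1 − ρ²).
- Ratio = (1 − ρ²) / [2(1 − ρ)] = (1 + ρ)/2. The SD cancels.

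| ρ | Variance ratio | Variance cut | SE cut | Equivalent sample multiple | Power, if 80% unadjusted |
|---|---|---|---|---|---|
| 0.3 | 0.65 | 35% | 19% | 1/0.65 = 1.54 | 93.5% |
| 0.5 | 0.75 | 25% | 13% | 1/0.75 = 1.33 | 89.9% |
| 0.7 | 0.85 | 15% | 8% | 1/0.85 = 1.18 | 86.0% |

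The last column is Φ[(1.960 + 0.842)/√ratio − 1.960]. At ρ = 0.3 this is Φ(2.802/0.806 − 1.960) = Φ(1.515) = 93.5%. If the SDs differ, the gain vanishes only where ρ × (post-dose SD / baseline SD) = 1.

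**Step 2: the outcome actually planned.** A maximum over several readings does not follow the Step 1 formula. It was simulated with baseline, end-of-infusion and 24-hour values trivariate normal with equal SDs, using 500,000 draws for each of seven correlation sets. Baseline to end of infusion ran from 0.3 to 0.9, and baseline to 24 hours from 0.2 to 0.7. The variance ratio is 1 − corr(baseline, deviation)². Each set was run with no mean change, and with an assumed mean fall of 0.5 SD at end of infusion and 1 SD at 24 hours.

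| Reading of maximum deviation | Variance ratio | Variance cut |
|---|---|---|
| Largest fall, or signed largest deviation | 0.55 to 0.83 | 17% to 45% |
| Absolute value, no mean change | 1.00 | nil |
| Absolute value, assumed mean fall | 0.78 to 0.87 | 13% to 22% |

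The nil result is a matter of symmetry. With no mean change, high baselines produce large falls and low baselines produce large rises, so an absolute deviation has no linear relation to baseline.

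**Step 3: chance imbalance.** With 560 per arm, the SE of the baseline difference is √(2/560) = 0.06 SD. In a single change score the fraction carried into the estimate is 1 − ρ: 0.06 × 0.7 = 0.042 SD at ρ = 0.3, and 0.06 × 0.3 = 0.018 SD at ρ = 0.7. This is already part of the variance difference in Step 1, not an addition to it.

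**The case against.** **The gap may be one of wording.** All the named terms are categorical, so calling the model ANCOVA suggests that a baseline covariate was taken for granted, and the list need not be exhaustive. This does not hold up. SAP 8.2 counts its factors as three, and SAP 7.3.1 spells out the covariates for its other ANCOVA. As written, baseline is not prespecified.

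**The simple formula describes a different outcome.** This stands. The 15% to 35% figure belongs to a single change score. For the planned maximum the gain runs from nil to about 45%, depending on a definition that the plan does not give. Adding the covariate alone might achieve nothing if the deviation is absolute.

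**This model is not the only look at hypotension.** Also true. SAP 8.1 tabulates events of special interest with onset within 120 minutes after the end of infusion, Appendix 1 (Table A-2) lists hypotension terms, and Protocol 10.2.2 requires hypotension to be recorded as an adverse event. Those summaries are descriptive, so the model in SAP 8.2 remains the only inferential BP comparison, but it does not carry the question alone.

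**Stronger readings.** A reader might infer that the drug has a known hypotensive effect which this test is set up to miss. The documents do not support that. Protocol 10.2.3 raises a possibility from animal findings at higher doses, the Phase 2 figures of 6% and 10% come without a p-value, and Protocol 4.4.3 concludes that no safety concerns were identified. Nor is the estimate systematically biased: under randomization an unadjusted change-score comparison is unbiased.

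**Conclusion.** The point holds as a minor, free improvement. The stated model omits a covariate that the trial already collects, and adding it ranges from essentially harmless to a useful gain in precision. The ranges in the working rest on normality, equal SDs and assumed correlations; the 13% to 22% range for an absolute deviation also needs an assumed mean fall. Protocol Appendix 1 makes a fall plausible, since it notes that pressure often drops after reperfusion, but it gives no amount.

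The undefined sign matters as much as the covariate. It decides whether adjustment helps at all, and an absolute deviation would pool rises with falls in an analysis whose main interest is falls.

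No stopping rule, sample size or primary conclusion depends on this analysis. The leading safety outcomes are serious adverse events and 90-day mortality.

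**What to change.** Before unblinding:

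- In SAP 8.2, add pre-dose systolic BP as a continuous covariate in the systolic model, and pre-dose diastolic BP in the diastolic model, using the SAP 1.7 definition of baseline.
- In the same edit, define maximum deviation as a signed quantity, for example the largest fall from baseline to 24 hours, and state which readings contribute.
- Align Protocol 11.9.4 so that both documents give the same model.

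The cost is a short text change and one degree of freedom per model out of more than 1000. No new data are needed.

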8.3 Laboratory and 12-Lead Electrocardiogram Results

CBC, electrolytes, INR, aPTT, serum creatinine and serum glucose will be reported at 24 ± 12 hours. A 12-lead ECG will be performed at Baseline or, if the treating physician deems that an ECG will impede the subject's access to care, within 6 hours of randomization, and at 24 ± 12 hours.

Absolute values for laboratory results and generalized 12-lead ECG results (i.e., normal, sinus bradycardia, etc.) will be summarized descriptively. Inferential statistics (ie, p-values or CI) will not be provided for these data.

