6.1.4.1 Guidance on Definitions of Selected Safety Outcomes

Symptomatic intracranial hemorrhage (ICH) defined according to the Heidelberg classification, as a new ICH [intracerebral hemorrhage, SAH, intraventricular hemorrhage (IVH), subdural hematoma (SDH)] associated with clinical evidence of neurological worsening, in which, the hemorrhage is judged to be the most important cause of the neurological worsening. Clinical worsening will be guided by the NIHSS score of a minimum of two or more points different from baseline.

Major extracranial hemorrhage defined as life-threatening, resulting in hemodynamic compromise or hypovolemic shock, requiring inotropic support or other means to maintain cardiac output, requiring blood transfusion of more than two units of packed red blood cells, or associated with a fall in hemoglobin greater than or equal to 5 g/L.

Contrast media-induced nephropathy will be defined as a rise of the serum creatinine of ≥ 0.5 mg/dl (≥ 44 mmol/l) or a $\geq 25\%$ increase from baseline pre-treatment level within 3 days after the endovascular procedure without an alternative etiology. Any creatinine measurements conducted as part of the protocol or standard of care in the first 3 days after the endovascular procedure in patients suspected by their treating physician of having a contrast nephropathy will be considered for this adjudication. .

Total radiation dose will be measured in mSv and recorded directly from the CT scanner. Dose-length product will be recorded directly from the CT scanner.

Malignant MCA infarction will be defined as any large infarction with mass effect observed on imaging where treatment (medical or surgical) is required for the treatment of mass effect.

Hemicraniectomy will be defined as that surgical procedure used to decompress the swollen hemisphere.

Vessel perforation will be defined at angiography by the operator and associated with sub-arachnoid hemorrhage.

Iatrogenic arterial dissection will be defined at angiography by the operator.

Arterial access site hematoma will be assessed as a complication of arterial access puncture and defined by clinical examination and anatomic imaging.

Retroperitoneal hematoma will be assessed as a complication of groin puncture and defined by imaging (ultrasound or CTA or MR).

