10.6.2 Biochemistry and Hematology

Blood work will be taken at baseline and at 24 hours including: CBC (hemoglobin, platelets and hematocrit), electrolytes (sodium, potassium, chloride), INR, aPTT, serum creatinine and serum glucose. This is described in [Sections 8.6. , 8.11](#) and the Schedule of Assessments.

If the subject is female and is of childbearing potential, a pregnancy test (urine or serum point-of-care pregnancy test) must be completed. Clinically significant laboratory findings from the 24-hour sample (post dose) will be recorded on the e-CRF as AEs.

10.7 12-Lead Electrocardiogram Monitoring.

A 12-lead ECG will be performed at Baseline or, if the treating physician deems that an ECG will impede the subject's access to care, within 6 hours of randomization, and at approximately 24 Hours. Clinically significant findings on the 24-hour ECG will be recorded on the e-CRF as AEs.

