11.9.5 Laboratory and 12-Lead ECG Results

Absolute values for laboratory results and generalized 12-lead ECG results (i.e., normal, sinus bradycardia, etc.) will be documented descriptively.

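### SAP 8.3 summarises laboratory results as absolute values only, so its by-arm summaries cannot show how many subjects' creatinine rose from their own baseline

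*SAP*

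**What the plan says.** SAP 8.3 gives the sampling time for the laboratory tests as follows: "CBC, electrolytes, INR, aPTT, serum creatinine and serum glucose will be reported at 24 ± 12 hours". It then sets the form of the summary: "Absolute values for laboratory results and generalized 12-lead ECG results (i.e., normal, sinus bradycardia, etc.) will be summarized descriptively". It excludes p-values and confidence intervals for these data. Protocol 11.9.5 is in the same terms: "Absolute values for laboratory results and generalized 12-lead ECG results (i.e., normal, sinus bradycardia, etc.) will be documented descriptively".

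The paired data exist. Protocol 10.6.2 states: "Blood work will be taken at baseline and at 24 hours including", and the list that follows contains serum creatinine. SAP 1.7 defines a subject's baseline as the "latest measurement taken prior to study drug administration".

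For vital signs, SAP 8.2 goes further: "Absolute values and changes for vital signs from pre-dose to Day 5 or discharge will be documented".

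The default form of a continuous summary is in SAP 6.0: "continuous data will be summarized for each treatment group using the number of observations (n), mean, standard deviation (SD), median, minimum, and maximum".

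Protocol 6.1.4.1 defines contrast nephropathy within 3 days of the procedure as "a rise of the serum creatinine of ≥ 0.5 mg/dl (≥ 44 mmol/l") or an increase of at least 25% from baseline, with no other cause. Only patients whom the treating doctor suspects of it are considered for that adjudication.

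**The concern.** Every subject receives study drug or placebo along with iodinated contrast, and creatinine is scheduled both before dosing and a day later. The natural descriptive question is how many subjects in each arm had a rise from their own starting value. The laboratory summaries in SAP 8.3 do not answer it.

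The other routes to a rise each leave something out:

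- **Nephropathy adjudication (Protocol 6.1.4.1)** covers suspected patients only, and the SAP does not mention it.
- **Adverse-event tables (SAP 8.1)** cover rises that an investigator judged clinically significant (Protocol 10.6 and 10.6.2).
- **The special-interest table (SAP 8.1 and Appendix 1)** includes acute kidney injury and renal failure, but only with onset within 120 minutes of the end of infusion. That is before the 24 ± 12 hour draw.
- **Subject listings (SAP 6.0)** hold both values but give no count by arm.

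What remains is a measured rise that nobody suspected or judged significant. At stake is the completeness of a descriptive safety display, not any tested hypothesis.

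**Working it through.** The plan states no figure on this point, so there is none to reproduce. The documents give no creatinine distribution either. The distributional inputs in steps 1 to 3 are therefore assumptions or constructions.

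**1. Dilution in the arm mean.** Suppose a fraction f of one arm rises by a proportion r, from average baselines, and nothing else changes. The arm mean moves by f × r.

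- f = 0.02, r = 0.50: 0.02 × 0.50 = 1.0%.
- f = 0.05, r = 0.50: 0.05 × 0.50 = 2.5%.

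With 560 per arm (SAP 1.4), 5% is 0.05 × 560 = 28 subjects. For scale, the standard error of a difference between two arm means, as a share of the mean, is CV × √(2/560) = CV × 0.0598. For an assumed between-subject CV of 0.25, 0.30 or 0.40 this is 1.5%, 1.8% or 2.4%. A 2.5% shift is then 1.7, 1.4 or 1.0 standard errors, which is hard to tell from chance by eye. A count row would show the 28 subjects directly.

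**2. The same absolute summaries fit very different counts.** Take log-creatinine with the same normal distribution at both times, s = √ln(1 + CV²), and within-subject correlation ρ. Then

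P(rise ≥ 25%) = 1 − Φ( ln 1.25 / (s √(2(1 − ρ))) ).

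For CV = 0.30, s = √ln 1.09 = 0.294 and ln 1.25 = 0.223:

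| ρ | s√(2(1−ρ)) | share rising ≥ 25% |
|---|---|---|
| 0.5 | 0.294 | 22.4% |
| 0.8 | 0.186 | 11.5% |
| 0.9 | 0.131 | 4.5% |
| 0.95 | 0.093 | 0.8% |

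Across CV 0.25 to 0.40 and ρ 0.5 to 0.95 the share runs from 0.2% to 28.1%. The absolute summaries carry no information on ρ, so they cannot yield the count.

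**3. Why change columns alone are not enough.** This is a construction to show possibility, not a forecast. Build an arm of 560 from 140 sets of four subjects with baselines 60, 75, 94 and 118 µmol/L. Let some sets move to 75, 94, 118 and 60, which is +25.0%, +25.3%, +25.5% and −49.2%.

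| Sets moved | Subjects meeting the limit | Mean change | SD of change |
|---|---|---|---|
| 0 | 0 (0%) | 0 | 0 |
| 14 | 42 (7.5%) | 0 | 10.65 |
| 140 | 420 (75%) | 0 | 33.67 |

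In every case, and at both times, n = 560, mean = 86.75, SD = 21.7, median = 84.5, minimum = 60 and maximum = 118. Mean change is also 0 throughout. Only a count states how many rose.

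**4. The SI threshold in Protocol 6.1.4.1.** Creatinine has a molar mass of 113.12 g/mol.

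- 0.5 mg/dl = 5 mg/L; 5 / 113.12 = 0.0442 mmol/L = 44.2 µmol/L.
- 44 mmol/L × 113.12 / 10 = 497.7 mg/dl, and 497.7 / 0.5 = 995.

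The printed SI figure is therefore about 1000 times the intended one. The two limbs of the definition meet at a baseline of 0.5 / 0.25 = 2.0 mg/dl (177 µmol/L). Below that, the 25% limb is reached first. The slip would thus matter only for a subject with a baseline above 177 µmol/L whose values are judged against the SI figure.

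**The case against.** The strongest reply is that this is a preference for a fuller table. The two documents agree with each other, and planning changes for vital signs creates no duty to plan them for laboratory tests. The leading safety outcomes are SAEs and 90-day mortality. All post-dose chemistry must be reviewed. Findings judged clinically significant become adverse events and are tabulated by arm, by preferred term, severity and relatedness. That judgement is made blind, so it should filter both arms alike. Phase 2 found no noteworthy laboratory differences, and Protocol 8.3 regards the renal risk of modern contrast as very low. The construction in step 3 needs one subject in each moved set to fall by 49% in about a day, which is not realistic. The proposed row also borrows a limit that the protocol applies over 3 days, to suspected cases, after excluding other causes.

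Most of this stands and sets the grade. It leaves a gap all the same: a blind filter is fair to both arms but still removes the rises it does not select, and the dilution in step 1 needs no contrived pattern.

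Four stronger readings might be inferred, and the documents do not support them:

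- **That no by-arm output anywhere shows creatinine rises.** The adverse-event tables show those judged significant. The list of IDMC outputs that SAP 8.5 places in its Appendix A is not in the text available here. The point is confined to what SAP 8.3 and Protocol 11.9.5 describe.
- **That baseline laboratory values will not be reported.** SAP 8.3 names only the later time, but the protocol synopsis speaks of analysing both baseline and post-dose findings.
- **That a promised nephropathy table was dropped.** Protocol 6.1.4.1 sets out an adjudicated definition for suspected patients and promises no such table.
- **That NA-1 is suspected of renal harm.** The documents report no creatinine signal for it, and both arms receive contrast.

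**Conclusion.** The point holds within its limits. Among the analyses described in the available text, laboratory results are summarised as absolute values only. A creatinine rise that is neither suspected nor judged significant is counted in no by-arm laboratory summary in SAP 8.3. A subset of 5% rising by 50% would move the arm mean by about 2.5%, assuming average baselines and no other change. The unit slip in Protocol 6.1.4.1 is real but separate, and small in effect because the mg/dl figure beside it is right.

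This is an improvement the sponsor could make, not one it must make. No primary, secondary or leading safety conclusion depends on it.

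**What to change.** In SAP 8.3, for each laboratory test, report by arm the baseline value (SAP 1.7 definition), the 24-hour value, the change from baseline, and the number of subjects with both values. Add one row by arm: number and percentage of subjects with paired values whose scheduled 24-hour creatinine rose by at least 0.5 mg/dl (44 µmol/L) or by at least 25%. Label it a descriptive laboratory finding that is not adjudicated contrast nephropathy. Give no p-value or confidence interval, in line with SAP 8.3 as it stands. Leave the adjudication in Protocol 6.1.4.1 unchanged.

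At the next protocol revision, correct 44 mmol/l to 44 µmol/L in Protocol 6.1.4.1.

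The table costs SAP wording, some change columns and one row, all from data already collected, and needs no protocol amendment. The downside is that more mild rises will be reported in both arms, some of them ordinary variation or hydration effects. A single draw at 12 to 36 hours will also miss later rises.
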